4.4.2 Derivation rules

The following parameters will be derived:

- Medical history finding: not ongoing at screening (MH.MHENRTPT is 'BEFORE')
- Concomitant disease finding: still ongoing at screening (MH.MHENRTPT is 'ONGOING' or missing)

4.4.3 Presentation of results

Medical history and concomitant diseases will be tabulated separately by treatment and overall. Each table will show:

- The number and percentage of subjects with and without findings
- The number and percentage of subjects with findings by system organ class and preferred term

All medical history and concomitant diseases data will be listed separately.

4.5 PROCEDURES AND MEDICATIONS

4.5.1 Available data

All procedures are coded into system organ classes and preferred terms using the medical dictionary for regulatory activities (MedDRA). For each procedure start and stop date(time)s or ongoing flag are collected.

All medications are coded using WHO-DRUG. ATC selection is performed. ATC coding up to level 5 is available in the clinical database. For each medication, a start date(time) and stop date(time) or ongoing flag are collected.

--	--	--

4.5.2 Derivation rules

Based on their start and stop date(time), procedures and medications will be allocated to each phase during which they were performed/administered. A procedure/medication can therefore be reported in more than one phase.

Phases are defined in section 5.2.1. Procedures/medications with (partially) missing dates will be allocated to each phase unless the available parts of the procedure/medication start or stop date(time) provide evidence that the procedure/medication was not taken during that phase.

Based on their start and stop date(time) procedures and medications will be allocated to one of the following categories:

- Prior: the procedure/medication stopped prior to first study drug administration
- Maintained: the procedure/medication started before first study drug administration and was ongoing at first study drug administration
- Concomitant: the procedure/medication started at or after first study drug administration
- Post-treatment: the medication/procedure started on or after the start of follow-up phase

For procedures/medications with (partially) missing date(time)s not allowing allocation to any of the categories, a worst-case allocation will be done based on the available parts of the medication/procedure start or stop date(time). The medication/procedure will be allocated to the first category allowed by the available data, according to the following order:

- Concomitant
- Post-treatment
- Maintained
- Prior

Note: these procedures/medications will only be allocated to the phases that match the worst-case allocated category.

4.5.3 Presentation of results

Procedures:

The number and percentage of subjects with procedures and the number and percentage of subjects with procedures by system organ class and preferred term alphabetically sorted will be tabulated per category (prior, maintained, and concomitant); by treatment and overall (prior procedures only). Blank system organ classes, if any, will be shown as 'Not Available' in the tables.

Subjects having more than one procedure allocated to the same category within the same treatment, system organ class and preferred term will be counted only once.

All procedures data will be listed.

Medications:

The number and percentage of subjects with medications and the number and percentage of subjects with medications by anatomical main group (level 1), therapeutic subgroup (level 2), chemical subgroup (level 4), and generic term will be tabulated per category (prior, maintained, and concomitant); by treatment and overall (prior medications only). Blank ATC levels, if any, will be shown as 'Not Available' in the tables.

Subjects having more than one medication allocated to the same category within the same treatment, anatomical main group, therapeutic subgroup, chemical subgroup, and generic term will be counted only once.

All medications data will be listed.

4.6 EXPOSURE TO STUDY DRUG

4.6.1 *Available data*

For each study drug administration, the dates (time), the prescribed dose, the actual volume administered, rescue dose flag and issues occurred during dosing will be recorded.

4.6.2 *Presentation of results*

All exposure data will be listed.

5. GENERAL METHODOLOGY

5.1 ANALYSIS SETS

5.1.1 *Analysis sets*

The following analysis sets will be considered in the statistical analysis:

Enrolled Set (ENR): all subjects for whom *informed consent was signed*

Randomized Set (RND): all *randomized* subjects

Safety Set (SAF): all randomized subjects who receive *at least one dose of study drug*

Notes:

- Having signed an informed consent is defined as having a complete informed consent signature date in the database.
- Randomized is defined as having a randomization date in the database or any information to confirm randomization.
- Having received at least one dose of study drug is defined as having an exposure date or any information confirming exposure present in the database.

Unless stated otherwise, the SAF analysis set will be used for demographics and baseline characteristics tables. All listings will be presented for the Randomized Set, unless states otherwise in section [8.2](#).

In case of local major protocol deviations, only the affected data at the specific time point will be excluded from the applicable analysis sets.

5.1.2 *As planned versus as actual analysis*

For analyses done on the safety analysis set (excluding general characteristics analyses), the actual treatment of the subject will be considered. In addition, the actual treatment will be presented in the general and safety listings.

For all other analyses, the planned treatment will be used.

5.2 PHASES AND TIME POINTS

5.2.1 *Phases*

Adverse events, medications, and procedures will be allocated to phases. For assessments, the visit and time point labels indicated on the subject's case report form (CRF) will be used to allocate to the correct treatment.

Adverse events, procedures and medications:

Phase	Start	End
Screening	Date of signing the ICF, with 00:00 added as time part	First administration date(time) – 1 minute
Treatment	First administration date(time)	Last administration date(time) + 48 hours
Follow-up	End date(time) of treatment phase + 1 minute	Date of last contact, with 23:59 added as time part

Per definition, and for each subject, the first phase starts on the date of the earliest available ICF signature, with 00:00 added as time part. The last available phase ends on the date of last contact, with 23:59 added as time part.

All tables and listings will present treatments rather than phases.

AEs, medications and procedures will be allocated to phases as described in sections 3.1.2 and 4.5.2 respectively.

In addition to the analysis phases described above, a subject will be considered to have entered a specific study phase based on the below definitions:

- Initiation phase: all subjects in the safety set
- Escalation phase: all subjects receiving at least one dose higher than the initial dose
- Stabilization phase: all subjects who receive at least 2 consecutive doses without escalation
Note: Subjects can skip the escalation phase and directly enter the stabilization phase from the initiation phase.
- Weaning phase: all subjects who receive at least one dose lower than the previous
- Cessation phase: all subjects reaching the cessation dose (i.e. between 90-110% of the initial dose for CHF6563 or < 0.025 mg/kg for morphine) and having a decrease in dose frequency (only subjects receiving CHF6563, i.e. dosing frequency is decreased q24 hours)

Note: in addition to the above definitions, other information present in SDTM (i.e. flags or visits present indicating that a subject has entered a specific phase) could be used to determine whether a subject entered a specific phase. A phase (and all subsequent phases previously entered by the subject) will be considered discontinued whenever a subject discontinues the study during that study phase.

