2. EFFICACY AND PHARMACOKINETIC ANALYSES

2.1 PRIMARY EFFICACY ENDPOINT

According to the protocol, the primary efficacy endpoint of this study is:

- Duration of treatment defined as the number of hours from first dose of study drug administration until the last dose of study drug.

2.1.1 *Derivation rules*

Duration of treatment (hours) = date/time of last study drug administration – date/time of first study drug administration

2.1.2 *Presentation of results*

All data relevant to the primary efficacy endpoint will be listed.

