3.1.3 Presentation of results

Tables will present TEAEs and post-treatment AEs only. Pre-treatment AEs will only be listed.

An overview table will show the number and percentage of subjects with at least one event and the number of events by treatment for the following:

- TEAEs
- Serious TEAEs
- Non-serious TEAEs
- ADRs
- Serious ADRs
- Severe TEAEs
- TEAEs leading to study drug discontinuation
- TEAEs leading to death
- Peri-dosing TEAEs
- ADRs leading to study drug discontinuation
- ADRs leading to death
- Peri-dosing ADRs
- Post-treatment AEs

All AEs, including pre-treatment events and all coding information will be listed. AEs started after date of last study medication intake will be flagged. Blank system organ classes and preferred terms, if any will be shown as ‘Not Available’.

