4. GENERAL CHARACTERISTICS ANALYSES

4.1 SUBJECT DISPOSITION

The following subject data will be tabulated:

- The number of screen failures overall
- The number of subjects in each analysis set by treatment and overall
- The number and percentage of subjects for each analysis visit included in the list below by treatment and overall
 - Screening
 - Day 1
 - Every 5 days of the treatment phase (Day 5, Day 10, Day 15, ...)
 - Day of last dose
 - End of treatment visit
- The number and percentage of subjects who entered, completed or discontinued each study phase (initiation, escalation, stabilization, weaning and cessation)
- The number and percentage of subjects who completed or discontinued the study as documented on the study termination page and the number and percentage of subjects for each study discontinuation reason by treatment and overall

All information collected in the CRF concerning allocation, code breaking, study discontinuation and information on phases, dates of first signed informed consent, last visit and last contact (over the whole study) and comments will be listed.

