8. LIST OF TABLES AND LISTINGS

8.1 TABLES

Number	Title	Analysis Set	TLFs Library Template Number
GENERAL CHARACTERISTICS			
14.1.1.1	Screen Failures (Randomized Set) Tabulation of completion/discontinuation and the reason for discontinuation.	ENR	DST001
14.1.1.2	Disposition by Treatment (Randomized Set) Tabulation of completion/discontinuation and the reason for discontinuation.	RND	DST002
14.1.1.3	Analysis Sets (Randomized Set) Tabulation of the number of subjects in each of the analysis sets defined in the SAP.	RND	DST006
14.1.1.4	Attendance at Study Visits (Randomized Set) Tabulation of the number and percentage of subjects that attended to each planned study visit (only visits defined in section 4.1) by treatment.	RND	SVT001
14.1.1.5	Attendance at Study Phases (Randomized Set) Tabulation of the number and percentage of subjects that entered, completed or discontinued each study phase (initiation, escalation, stabilization, weaning and cessation). The template SVT002 is used replacing the treatment periods by the study phases.	RND	SVT002
14.1.1.6	Major Protocol Deviations (Safety Set) Tabulation of the major protocol deviations (at least one), deviation category and deviation type by treatment and overall.	SAF	DVT001
14.1.1.7	Minor Protocol Deviations (Safety Set) Tabulation of the minor protocol deviations (at least one), deviation category and deviation type by treatment and overall.	SAF	DVT001
14.1.2.1	Demographic Characteristics (Safety Set) Descriptive statistics of continuous parameters and frequency tabulation of categorical parameters.	SAF	DMT001
14.1.2.2	Baseline Characteristics (Safety Set) Frequency tabulation of baseline characteristics.	SAF	DMT001
14.1.2.3	FNAST Scores at Baseline (Safety Set) Descriptive statistics of FNAST scores at baseline.	SAF	BLT001
14.1.2.4	Maternal Smoking Status (Safety Set) Frequency tabulation of the maternal smoking status at screening.	SAF	SUT001
14.1.2.5	Feeding Status (Safety Set) Descriptive statistics of continuous parameters and frequency tabulation of categorical parameters.	SAF	BLT001

Number	Title	Analysis Set	TLFs Library Template Number
14.1.2.6	Head Circumference and Weight at Screening (Safety Set) Descriptive statistics of head circumference and weight at Screening.	SAF	BLT002
14.1.2.7	Vital Signs at Screening (Safety Set) Descriptive statistics of vital signs results at Screening.	SAF	BLT002

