8.2 LISTINGS

[figure not shown]
Number	Title	Analysis Set	TLFs Library Template Number
GENERAL CHARACTERISTICS			
16.1.7	Randomization Schedule (Randomized Set) Listing of subject numbers and randomization information All discrepancies (as-randomized versus as-treated) will be presented.	RND	DSL001
16.2.1.1 Screening Failures (Randomized Enrolled Set) Listing of all subjects that discontinued after randomization. The study discontinuation reason will also be listed.			
16.2.1.2	Study Discontinuation After Randomization (Randomized Set) Listing of all subjects that discontinued after randomization. The study discontinuation reason will also be listed.	RND	DSL003
16.2.1.3	Subject Disposition (Randomized Set) Listing of the reasons for completion / discontinuation and the number of days since first study drug administration at study discontinuation. In case the discontinuation was due to AE, the AE will be presented in this listing. If there is another explanation on the discontinuation reason collected in the CRF, this will also be presented in this listing.	RND	DSL004
16.2.1.4	Randomization Code Broken (Randomized Set) Listing of the code breaking information. Only subjects for which the code was broken are presented in this listing.	RND	DSL005
16.2.1.5	Analysis Set Disposition (Enrolled Set) Listing of all subjects and analysis set indicators.	ENR	DSL006
16.2.1.6	Subject Disposition: Analysis Phases and Periods (Enrolled Set) Listing of the phases and periods in the study together with the start and end date(time)s.	ENR	DSL008
16.2.1.7	Study Visits (Enrolled Set) Listing per subject number of all subject visits, together with the start and end date of each visit. Listing is sorted chronologically by visit start date within each subject.	ENR	SVL001
16.2.1.8	First and Last Contact in the Study (Enrolled Set) List of the date of the first signed ICF, last visit date and last date of contact in the study. All dates are presented overall, not by treatment.	ENR	
16.2.2.1	Violation of Eligibility Criteria (Enrolled Set) Only violated in- and exclusion criteria will be listed. Only deviations with DVDECOD = "VIOLATION OF INCLUSION CRITERION" or "VIOLATION OF EXCLUSION CRITERION" will be selected.	ENR	DVL001
16.2.2.2	Protocol Deviation (Enrolled Set) Listing of all protocol deviations information	ENR	DVL002

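### Does SAP v2.0 need its own rule for babies who stop study drug but stay in the study?

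*SAP*

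**What the plan says.** Protocol 12.3.2 (also 4.4 and the statistical part of the outline) allows study drug to be stopped while follow-up and data collection go on, and refers the handling to the SAP.

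SAP v2.0 touches these babies in five places:

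- **1.2 Estimand.** Leaving the study is the only intercurrent event with its own rule. All others fall under treatment policy, and the first example is use of other therapies.
- **2.1.1 Primary endpoint.** "Duration of treatment (hours) = date/time of last study drug administration" minus the time of the first one. No condition about finishing the course is attached. This agrees with protocol 8.1.
- **4.1 Disposition.** Babies are counted as having "completed or discontinued the study as documented on the study termination page".
- **5.2.1 Phases.** A phase "will be considered discontinued whenever a subject discontinues the study during that study phase". Entry to each phase is defined; for cessation it is "all subjects reaching the cessation dose" and, for CHF6563 only, also having the dosing interval lengthened. Completion of a phase is not defined.
- **8.1, Table 14.1.1.5.** "Tabulation of the number and percentage of subjects that entered, completed or discontinued each study phase".

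SAP 2.2.3 and 6.1 cancel all inference because 7 babies were randomized.

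**The concern.** The protocol promises a rule, and the SAP seems to give only a general clause. Suppose the parents have study drug stopped during escalation and the baby stays in follow-up. Read literally, no phase is discontinued in Table 14.1.1.5, the disposition table may show a study completer, and the primary listing prints a short duration with no mark on it.

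The trial is about how long treatment lasts. With testing gone, how many babies finished the course is one of the main descriptive facts left, and a short duration caused by stopping early could be read as a quick success. SAP 1.2 adds to the unease: it describes the variable as treatment for the syndrome, while 2.1.1 measures study drug only, and it still refers to 5.3.1 for an imputation that 5.3.1 now leaves to the data review.

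**Working it through.** The plan states no figure for this point, and the sample size does not depend on it. The check is whether the outputs that remain show an early drug stop, and what changes if one occurred.

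**1. Can the duration alone show it?** Shortest full courses from protocol 6.2.2.1 and 6.2.2.2, with no escalation and no weaning holds:

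- CHF6563: 48 h stabilization at 10 µg/kg, already inside the 90-110% window; 24 h at q12 gives 48 + 24 = 72 h; one q24 interval gives 72 + 24 = 96 h. Range 72-96 h.
- Morphine, each 15% taken from the current dose: 0.07 × 0.85^6 = 0.0264 and 0.07 × 0.85^7 = 0.0224 mg/kg, so seven steps. The seventh falls at 48 + 6 × 24 = 192 h, with up to 24 h at that dose: 192-216 h.
- Morphine, each 15% taken from the starting dose (0.0105 mg/kg): four steps leave 0.0280 and five leave 0.0175, so five steps. The fifth falls at 48 + 4 × 24 = 144 h: 144-168 h.

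So no. A duration beyond these times fits either a finished or an interrupted course. This part of the concern is right.

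**2. Can the phase table show it?** Every dosed baby enters initiation (5.2.1). Per arm:

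early drug stops among babies who stayed = entered initiation − entered cessation − left the study before cessation.

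The first two terms are in the entered column of Table 14.1.1.5. The third comes from its discontinued column and from listing 16.2.1.3, which gives "the number of days since first study drug administration at study discontinuation". Example with assumed counts: 7 enter initiation, 6 enter cessation, 0 leave the study before then; 7 − 6 − 0 = 1. The discontinued column reads 0, yet the early stop is visible.

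The cessation limit for morphine is strict in SAP 5.2.1 and includes equality in protocol 6.2.2.2. The two passages must be reconciled, but this does not disturb the count in the morphine example above: the unrounded doses pass from 0.0264 to 0.0224, or from 0.0280 to 0.0175, and neither path lands on 0.025.

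**3. Can the case be identified?** Listing 16.2.5.1 shows every administration with its time, prescribed dose and volume; SAP 4.6.1 adds that the "rescue dose flag and issues occurred during dosing will be recorded". Medications with start and stop times are in 16.2.4.12 and comments in 16.2.4.13. Stops caused by adverse events have their own line, "TEAEs leading to study drug discontinuation", in Table 14.3.1.1 and their own listing, 16.2.7.8.

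**4. Size.** One such baby is 1/7 = 14.3% of those randomized; none gives zero. Tests, intervals and arm means affected: none, because none is produced.

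**5. The SAP 1.2 wording.** With assumed times (study drug stopped at 72-240 h, another opioid continued to 360-720 h), the listed value would be between 72/720 = 10% and 240/360 = 67% of a duration counting all treatment. That gap would matter for a mean. SAP v2.0 computes no mean, and the listed value follows protocol 8.1.

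**The case for a change.** The best argument for a change is that the protocol made a specific promise and a general clause does not keep it. The treatment-policy sentence belongs to an estimand whose analysis is cancelled, and it says nothing about counting phases. Two retained tables could also seem to disagree: protocol 7.1.3 has study treatment discontinued for a confirmed QTc of 500 ms or more without saying that the baby leaves the study. Such a baby could count as an adverse-event drug stop in one table and show no discontinued phase in another. A parent-requested stop has no dedicated output at all.

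Much of this stands as description. Completion of a phase is undefined, no flag is specified, and the reason for a stop unrelated to an adverse event may appear only in comments. The subtraction above also misses a baby who stops after entering cessation, and it needs the exposure dates for one who stops drug and later leaves the study.

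It does not follow that a count is wrong. The two tables answer different questions, leaving the study and stopping the drug, and each is right under its own definition. How the termination page would code these babies cannot be seen from the documents, so their being shown as completers is a supposition. With at most seven dosing records to read, an analyst can settle each case at the data review and add a footnote.

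**Conclusion.** No change is called for. The plan lacks detail here, but the gap is one that analysts fill sensibly from data already listed: non-entry into cessation gives the count, and the exposure listing gives the time of the stop. The effect is zero if no baby stopped drug and stayed. If one did, one descriptive column differs by 1 of 7 (14.3%) from what a wider definition would give, and no conclusion moves. The wording of the variable and the leftover cross-reference in SAP 1.2 are clerical, since no analysis now uses them.

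This rests on three things: inference stays cancelled, as SAP 6.1 states; the exposure and medication listings are complete; and the general clause in SAP 1.2 is read as covering these babies. SAP v1.0 is not available, so nothing is said about the rule it may have held. Had the planned comparison in 57 babies gone ahead, the choice between study-drug duration and total treatment duration would have needed an explicit rule.

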5.2.2 Baseline and change from baseline

The baseline value is a non-missing value before the first administration of any study drug.

Unless otherwise specified, Screening will be used as the baseline measurement. In case there are no assessments/measurements at Screening, the baseline value will be set to missing.

The following table summarizes the baseline definition for each parameter:

Parameter	Baseline
Vital signs	Screening
Head circumference and body weight	Screening
Biochemistry, hematology and liver function	Screening
FNAST scores	Last non-missing value before the first administration of any study drug

Change from baseline is defined as:

Change from baseline at time point t = value at time point t – baseline value.

5.2.3 *Relative day*

Relative days (DY) will be calculated according to the following rule:

- Concerned date < reference date: DY = concerned date – reference date
- Concerned date \geq reference date: DY = concerned date – reference date + 1

The reference date is the date of first administration of study drug

5.2.4 *Analysis visits*

The analysis will use the visits indicated on the subject's CRF. In addition, the vital signs assessments will be allocated to analysis time point windows as defined below based on the actual time of the assessment relative to the first dose (note: time points are not collected on the subject's CRF).

The screening value is the last available and non-missing value before the randomization visit (Day 1). This value corresponds to the screening visit, except in case of retesting. Reason for this approach is the use of retest results for subject eligibility assessment.

Unscheduled assessments will not be used in the analysis unless an unscheduled assessment was done to replace unavailable/unreliable data. The decision whether an unscheduled assessment should be used instead of the original assessment will be taken during the data review meeting before database lock. The selection of the unscheduled assessments to be included in the analysis instead of the original assessments will be done in the corresponding ADaM datasets using appropriate values for AVISIT(N) and ATPT(N). Hard coding (documented in the DRR and by a Note to File signed off by both [REDACTED] and Chiesi Farmaceutici S.p.A) will be implemented in the impacted analysis programs by including a comment.

Baseline is defined in section 5.2.2.

Scheduled and unscheduled assessments will be listed.

Follow-up visits will be summarized at selected time points only. All follow-up data will be listed.

The analysis visit labels will be assigned using the following rules:

- All planned screening, re-screening, eligibility recheck, etc. visits occurred during the screening phase will be presented as 'Screening'.

- All planned visits occurred during a scheduled day, will be presented as 'Day x' (x = study day, e.g. 'Day -1', 'Day 1', etc.)
- Early termination visits will be presented as 'Early Termination'
- Follow-up visits will be presented as 'Follow-up'. In case recurrent follow-up visits are planned, the label will include details of the repeated follow-up (e.g. 'Follow-up Day 1', 'Follow-up Week 2', etc.)
- Unscheduled visits that occurred during a planned visit day will be presented with the same label as the planned visit (see rules above)
- Unscheduled visits that occurred on a day different than a planned visit will be presented as 'Unscheduled'
- Other visits not covered by the rules above will be presented using similar labels to the ones used in SDTM (XX.VISIT)

